#### **9.4.4.2 Secondary endpoints and additional key secondary endpoints**

To assess the PD effect of SOBI003 on HS levels in CSF, serum and urine, linear models are used to model the change from baseline in HS levels as dependent variable, for both logged HS levels and untransformed HS levels, and baseline level and age as continuous covariates, and accumulated dose as covariate and sex as factor. The analyses are conducted for each assessment time point. In addition, linear analyses with HS levels, both logged HS levels and untransformed HS levels, in CSF, serum and urine, as dependent variable, and baseline level and age as continuous covariates, and dose and sex as factors will be performed across all assessments, with assessment as a repeated factor.

Adaptive behavior will be analyzed with the same repeated measures model as DQ, but adapted for one group (i.e. no treatment\*visit interaction term), the SOBI003 group.

PK results are presented by dose level using descriptive statistics. In addition, results are presented by demographic characteristics, e.g., age-group and bodyweight, as applicable.

Immunogenicity is summarized using frequency counts and percentages by dose level. To assess the PD effect of SOBI003 on MRI, linear models are used to model the change from baseline in MRI as dependent variable, for both logged MRI and untransformed MRI, and baseline level and age as continuous covariates, and accumulated dose (including the FIH study) as covariate and sex as factor. The analyses are conducted for each assessment time point i.e. Weeks 52 and 104.

In addition, linear analyses with MRI levels, both logged MRI levels and untransformed MRI levels, as dependent variable, and baseline level and age as continuous covariates, and accumulated dose as covariate and sex as factor will be performed across all assessments (including the FIH study), with assessment as a repeated factor.

Endpoints relating to the neurocognition, adaptive behavior, liver and spleen volume, QoL, language, motor function and sleep pattern are summarized using descriptive statistics.

#### **9.4.5 Multiple comparison procedure**

A hierarchical approach will be used for the key secondary co-endpoints.

The primary analysis will be based on a 2-sided test using a significance level of 0.05. A stepwise sequential testing procedure will be used to ensure a multiple level of significance of 0.05.

- 1st step: The null hypothesis of no difference between the treatments with respect to the reduction from baseline HS in CSF at 24 months will be tested using a significance level of 0.05. If the null hypothesis is rejected, then it will be concluded that SOBI003 reduces HS. Furthermore, the 2nd step of the sequential testing procedure will be performed.
- 2nd step: The null hypothesis of no difference between the treatments with respect to the change in DQ score at 24 months will be tested using a significance level of 0.05. If the null hypothesis is rejected, it will be concluded that SOBI003 improves cognitive function as compared to untreated patients.

This multiple comparison procedure controls that the multiple level of significance is no more than 5%.

Formally, the second confirmatory step will only be valid after the 1st step has been successfully met.

#### **9.4.6 Analysis related to exploratory objectives**

Continuous variables are summarized using the number of patients, the mean, the standard deviation, the median, the minimum value, and the maximum value. Categorical variables are summarized using frequency counts and percentages.

#### **9.4.7 Analysis of safety and tolerability data**

##### **9.4.7.1 Adverse events**

Reported AE(s) during the study are coded using MedDRA and severity of AEs is graded using NCI CTCAE v.03. The number of patients with any AE are is summarized in frequency tables by treatment dose level, body system, preferred term, relation to IMP and maximum severity. Listings of AE subgroups such as SAE(s) and AEs leading to discontinuation are also presented.

##### **9.4.7.2 Physical examination**

All physical examination records will be listed.

##### **9.4.7.3 Neurological examination**

All neurological examination records will be listed.

##### **9.4.7.4 Laboratory variables**

Laboratory test results will be compared to laboratory reference ranges, and values outside of the applicable range will be flagged as high (H) or low (L). The laboratory test results will be listed for each subject and summarized by descriptive statistics.

#### **9.4.7.5 Vital signs**

Vital sign results will be compared to reference ranges, and values outside the applicable range (including clinically important change and orthostatic change values) will be flagged as high (H) or low (L). The vital sign results will be listed for each subject and summarized by descriptive statistics.

#### **9.4.7.6 ECG**

12-lead ECGs are obtained at Weeks 52 and 104, and during Early Termination. ECG machines Mortara ELI 250c with VERITASTM resting ECG interpretation algorithm will be provided to the sites. The ECGs will be listed for each subject.

#### **9.4.8 Interim analysis**

No interim analysis is planned for this study.

#### **9.4.9 Multiple comparison/multiplicity**

Since no multiple hypothesis tests will be performed, there will be no adjustments for multiplicity.

#### **9.4.10 Handling of missing data**

All missing DQ values will be imputed. A sensitivity analysis will be performed where no imputations are performed, but all values are used: If a patient has a missing DQ score in any assessment, then the same patient's non-missing scores will be used in the repeated measures model (see Section 9.4.4). The repeated measures model handles missing values based on the MAR assumption. One further sensitivity analysis will address this assumption based on zero imputations. Another sensitivity analysis for this purpose will be a tipping point analysis.

## **10 Data collection, handling and record keeping**

### **10.1 Data standards**

Collection of data should be performed in the Clinical Data Acquisition Standards Harmonization (CDASH) format, according to the Clinical Data Interchange Standards Consortium (CDISC). The standards should be used to the extent possible and/or required for the specific study/project. The minimum requirement of the CDISC standard is to collect all core variables specified as 'Required' in the Study Data Tabulation Model (SDTM) format.

### **10.2 Case report form**

A CRF is required and should be completed for each included patient. In this study an electronic CRF will be used. The completed original CRFs are the sole property of Sobi and

should not be made available in any form to third parties, except for authorized representatives of appropriate regulatory authorities, without written permission from Sobi.

It is the responsibility of the investigator to ensure completion and to review and approve all CRFs. CRFs must be signed electronically by the investigator. These signatures serve to attest that the information contained on these CRFs is correct. At all times, the investigator has final responsibility for the accuracy and authenticity of all clinical and laboratory data entered on the CRFs.

### **10.3 Source data**

Patient source documents are the physician's patient records maintained at the study site. In most cases, the source documents will be the hospital's or the physician's chart. In those cases, the information collected on the CRFs must match those charts. For the MRIs and actigraph assessments, the digital files are the source. For ECG the print-outs are the source. For the VABS-II, BSID-III and the KABC-II, the completed test forms and the central reader's confirmation of total scores and age-equivalence scores are the source.

### **10.4 Database closure**

Prior to database closure, all tasks or criteria defined in the data management plan must be completed and documented. The study database must be locked before generation of any final results. The database lock will be approved by relevant study personnel and all edit accesses will be removed. The study database can only be unlocked in case critical errors, affecting the main conclusions of the study, are discovered.

### **10.5 Record retention**

To enable evaluations and/or audits from Health Authorities and/or Sobi (or delegates), the investigator agrees to keep records in accordance with the essential documents defined in the ICH GCP Guidelines (1), including the identity of all participating patients (sufficient information to link records, e.g., CRFs and hospital records), all original signed informed consent forms, copies of all paper CRFs (i.e., completed paper questionnaires and BSID-III/KABC-II assessments forms), an archival copy on compact disc of the electronic CRFs provided by INC Research and detailed records of IMP accountability. The records should be retained by the investigator according to local regulations or as specified in the Clinical Trial Agreement.

If the investigator relocates, retires, or for any reason withdraws from the study, the study records may be transferred to an acceptable designee, such as another investigator, another institution, or to Sobi. The investigator must obtain Sobi's written permission before disposing of any records.

## **11 End of study**

The end of this study is defined as the date of last patient out, i.e., the last patient's last visit.

## **12 Sponsor's discontinuation criteria**

Sobi reserves the right to discontinue the study prior to inclusion of the intended number of patients, but intends only to exercise this right for valid scientific or administrative reasons. After such a decision, the investigator must contact all participating patients within 2 weeks. All study materials must be collected and all the CRFs completed to the greatest extent possible.

## **13 Dissemination and publication of results**

Sobi will register the study and post study results regardless of outcome on a publicly accessible website in accordance with applicable laws and regulations, e.g. on [www.clinicaltrials.gov](http://www.clinicaltrials.gov) and EudraCT.

Sobi follows the principles of the International committee of medical journal editor's recommendations for the conduct, reporting, editing, and publication of scholarly work in medical journals (23). After completion of this study, the data may be considered for reporting at a scientific meeting or for publication in a scientific journal. The sponsor will be responsible for these activities and will work with the investigators to determine how the publication is written, the number and order of authors, the journal or scientific meeting to which it will be submitted, and other related issues. The results of the study, or any part thereof, shall not be published without the prior written consent and approval of Sobi, such consent and approval not to be unreasonably withheld.

15.2.5	Adverse Events by Relationship to Study Drug	26
15.2.6	Deaths	26
15.3	Laboratory data	26
15.4	Vital signs	26
16	Pharmacokinetics and Immunogenicity	27
16.1	Pharmacokinetic Parameters	27
16.2	Immunogenicity	28

17	The primary analysis for the pivotal phase 3 study	29
18	References.....	30

Table of figures

Figure 1	Overview for study design for study SOBI003-002	11
----------	---	----

Table of tables

Table 1	Partial date derivation	15
Table 2	Selection of neurocognitive assessment method.....	16

1 Abbreviations and definition of terms

ADA	Anti-drug antibody
AE	Adverse event
AEq	Age-equivalent score
AUC	Area under curve
BSID-III	Bayleys Scales of Infant and Toddler Development®, third edition
CL	Clearance
CNS	Central nervous system
CSR	Clinical study report
DQ	Development quotient
FAS	Full analysis set
FIH	First time in human
HS	Heparan sulfate
IMP	Investigational medicinal product
KABC-II	Kaufman assessment battery for children, second edition
MPS IIIA	Mucopolysaccharidosis type IIIA
MAR	Missing at random
MRI	Magnetic resonance imaging
NH	Natural history
NVI	Nonverbal index
SAE	Serious adverse event
SAP	Statistical Analysis Plan
SRC	Safety review committee
Sobi	Swedish Orphan Biovitrum
TEAE	Treatment emergent adverse event
PPS	Per Protocol Set
VABS-II	Vineland adaptive behavior scales, second edition

2 Introduction

This Statistical Analysis Plan (SAP) describes the planned analysis and reporting for Sobi protocol SOBI003-002 (An open, single-arm, multicenter extension study to assess the safety, tolerability and efficacy of long-term SOBI003 treatment in pediatric MPS IIIA patients).

This extension study is being completed to assess the efficacy and safety of SOBI003 for the treatment of MPS IIIA in pediatric patients.

The purpose of this SAP is to outline the planned analyses to be completed to support the Clinical Study Report (CSR) for protocol SOBI003-002. The planned analyses identified in this SAP will be included in regulatory submissions and/or future manuscripts. Also, exploratory analyses not necessarily identified in this SAP may be performed to support the clinical development program. Any post-hoc, or unplanned, analyses not identified in this SAP will be clearly identified in the respective CSR. This SAP also includes a description of upcoming Phase III analyses, see Section 17.

The structure and content of this SAP provides sufficient detail to meet the requirements identified by the FDA and International Conference on Harmonization of Technical Requirements for Registration of Pharmaceuticals for Human Use (ICH): Guidance on Statistical Principles in Clinical Trials. All work planned and reported for this SAP will follow internationally accepted guidelines, published by the American Statistical Association and the Royal Statistical Society, for statistical practice.

3 Study objectives and endpoints

3.1 Primary objective

The primary objective is:

- To assess the long-term safety and tolerability of SOBI003

3.2 Key secondary objectives

- To evaluate the efficacy of SOBI003 on neurocognitive function, as compared to untreated MPS IIIA patients from a NH control.
- To evaluate the effect of SOBI003 on HS levels in CSF

3.3 Secondary objectives

The secondary objectives are:

1. To assess the effect of SOBI003 on adaptive behavior, as compared to untreated MPS IIIA patients from a NH control
2. To assess the effect of SOBI003 on HS levels in serum and urine

3. To assess the effect of SOBI003 on brain magnetic resonance imaging (MRI) abnormalities
4. To assess the effect of SOBI003 on liver and spleen volume
5. To assess the effect of SOBI003 on Quality of Life
6. To assess the effect of SOBI003 on language
7. To assess the effect of SOBI003 on motor function
8. To assess the effect of SOBI003 on sleep pattern
9. To assess the immunogenicity of SOBI003
10. To characterize steady-state pharmacokinetics (PK) of SOBI003 by the use of non-compartmental analysis (NCA)

3.4 Exploratory objectives

The exploratory objectives are:

1. To assess the effect of SOBI003 on adaptive behavior over time
2. To characterize the PK properties of SOBI003 following repeated administration by the use of population PK analysis
3. To evaluate the PK/PD relationship between SOBI003 concentrations in serum and effect of SOBI003 on HS levels in CSF, serum and urine by the use of population modelling analysis
4. To evaluate the PK/PD relationship between SOBI003 concentrations in serum and CSF, and the effect of SOBI003 on other biomarkers than HS and neuro-cognitive measures eg. DQ, as well as MRI data, by the use of population modelling

As local regulations permit and provided that additional separate caregiver consent is given, the exploratory objectives are also to:

- Collect and store serum and CSF samples to enable analyses of biomarkers with possible relation to safety, tolerability, immunogenicity, PK and PD of SOBI003, as identified in future

3.5 Study endpoints

3.5.1 Primary endpoint

The primary endpoint to evaluate the safety and tolerability of SOBI003 is:

- Treatment Emergent Adverse Events (TEAEs) and Serious Adverse Events (SAEs)

3.5.2 Secondary endpoints related to the primary objective

The secondary endpoints to evaluate the safety and tolerability of SOBI003 are:

- Vital signs (blood pressure, heart rate, body temperature, respiratory rate and pulse oximetry)
- Laboratory safety variables (hematology, coagulation, clinical chemistry and urine analysis)

3.5.3 Key secondary endpoints

Study efficacy evaluation will primarily be based on:

- Change from baseline at Week 104 in Development Quotient (DQ) as assessed by the Bayley Scales of Infant and Toddler Development®, third edition (BSID-III) cognitive subtest or the Kaufman Assessment Battery for Children, Second edition (KABC-II)
- Change from baseline at Week 104 in CSF HS

Additional key secondary endpoints are:

- Change from baseline at Week 52 in Development Quotient (DQ) as assessed by the Bayley Scales of Infant and Toddler Development®, third edition (BSID-III) cognitive subtest or the Kaufman Assessment Battery for Children, Second edition (KABC-II)
- Change from baseline at Weeks 52 and 104 in Age Equivalent (AEq) as assessed by the Bayley Scales of Infant and Toddler Development®, third edition (BSID-III) cognitive subtest or the Kaufman Assessment Battery for Children, Second edition (KABC-II)
- Change from baseline at Week 52 in CSF HS

3.5.4 Secondary endpoints

The endpoints relating to the 1st secondary objective are:

- Change from baseline at Weeks 52 and 104 in adaptive behavior age-equivalence score (AEq) as assessed by Vineland Adaptive Behavior Scales, Second edition (VABS-II)
- Change from baseline at Weeks 52 and 104 in adaptive behavior composite score as assessed by Vineland Adaptive Behavior Scales, Second edition (VABS-II)

The endpoints relating to the 2nd secondary objective are:

- Change from baseline at Weeks 52 and 104 in serum HS
- Change from baseline at Weeks 52 and 104 in urine HS

The endpoints relating to the 3rd secondary objective are:

- Change from baseline at Weeks 52 and 104 in gray matter volume as assessed by brain volumetric MRI
- Change from baseline at Weeks 52 and 104 in compound ventricular volume as assessed by brain volumetric MRI
- Change from baseline at Weeks 52 and 104 in fractional anisotropy (FA) and mean diffusivity (MD) of corpus callosum as assessed by diffusion tensor imaging MRI

- Change from baseline at Weeks 52 and 104 in FA and MD of cerebral white matter as assessed by diffusion tensor imaging MRI
- Change from baseline at Weeks 52 and 104 in cerebral white matter as assessed by susceptibility weighting imaging (SWI) MRI
- Change from baseline at Weeks 52 and 104 in basal ganglia as assessed by SWI MRI

The endpoints relating to the 4th secondary objective are:

- Change from baseline at Weeks 52 and 104 in liver volume as assessed by abdominal MRI
- Change from baseline at Weeks 52 and 104 in spleen volume as assessed by abdominal MRI

The endpoints relating to the 5th secondary objective are:

- Change from baseline at Weeks 52 and 104 in Pediatric Quality of Life inventory (PedsQL) total score

The endpoints relating to the 6th secondary objective are:

- Change from baseline at Weeks 52 and 104 in expressive language AEq score as assessed by the BSID-III language subtests or the KABC-II Expressive Vocabulary subtest, and the VABS-II communication domain
- Change from baseline at Weeks 52 and 104 in receptive language AEq score as assessed by the BSID-III language subtests or the KABC-II Expressive Vocabulary subtest, and the VABS-II communication domain

The endpoints relating to the 7th secondary objective are:

- Change from baseline at Weeks 52 and 104 in gross motor function AEq score as assessed by the BSID-III motor subtests and the VABS II
- Change from baseline at Weeks 52 and 104 in fine motor function AEq score as assessed by the BSID-III motor subtest and the VABS-II

The endpoints relating to the 8th secondary objective are:

- Change from baseline at Weeks 52 and 104 in sleep pattern as assessed by the Children's Sleep Habits Questionnaire (CSHQ) score
- Change from baseline at Weeks 52 and 104 in sleep-related variables as assessed by actigraphy (including total sleep time, total day- and night time sleep duration, sleep latency, sleep efficiency, number of nocturnal awakenings, and wake after sleep onset)

The endpoints relating to the 9th secondary objective are:

- Occurrence of Anti-drug antibody (ADA) against SOBI003 in serum at Weeks 39, 52, 78 and 104, and adjacent to dose adjustments (seroconversion rate, time to seroconversion, transient/persistent). For patients with confirmed ADA positive serum samples, the following additional endpoints apply; ADA titers and IgG subclasses in serum, and presence of neutralizing antibodies (NAb) in serum.
- Occurrence of ADAs against SOBI003 in CSF at Weeks 39, 52, 78 and 104 (conversion rate, time to occurrence, transient/persistent). For patients with confirmed ADA positive

CSF samples, the following additional endpoints apply: ADA titers and presence of NAb in CSF.

The endpoints relating to the 10th secondary objective are:

- Serum SOBI003 PK parameters at Weeks 38, 52, 78 and 104, and adjacent to dose adjustments; $t_{\text{End of inf}}$, $C_{\text{End of inf}}$, $C_{\text{Pre-dose}}$, CL, AUC_{0-168h}
- SOBI003 concentrations in CSF pre-dose at Weeks 52 and 104.

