### 6.3.1 Secondary endpoints

The endpoints relating to the 1st secondary objective are:

- Change from baseline at Weeks 52 and 104 in adaptive behavior age-equivalence score (AEq) as assessed by Vineland Adaptive Behavior Scales, Second edition (VABS-II)

The endpoints relating to the 2nd secondary objective are:

- Change from baseline at Weeks 52 and 104 in serum HS
- Change from baseline at Weeks 52 and 104 in urine HS

The endpoints relating to the 3rd secondary objective are:

- Change from baseline at Weeks 52 and 104 in gray matter volume as assessed by brain volumetric MRI
- Change from baseline at Weeks 52 and 104 in compound ventricular volume as assessed by brain volumetric MRI
- Change from baseline at Weeks 52 and 104 in fractional anisotropy (FA) and mean diffusivity (MD) of corpus callosum as assessed by diffusion tensor imaging MRI
- Change from baseline at Weeks 52 and 104 in FA and MD of cerebral white matter as assessed by diffusion tensor imaging MRI
- Change from baseline at Weeks 52 and 104 in cerebral white matter as assessed by susceptibility weighting imaging (SWI) MRI
- Change from baseline at Weeks 52 and 104 in basal ganglia as assessed by SWI MRI

The endpoints relating to the 4th secondary objective are:

- Change from baseline at Weeks 52 and 104 in liver volume as assessed by abdominal MRI
- Change from baseline at Weeks 52 and 104 in spleen volume as assessed by abdominal MRI

The endpoints relating to the 5th secondary objective are:

- Change from baseline at Weeks 52 and 104 in Pediatric Quality of Life inventory (PedsQL) total score and PedsQL™ Family Impact Module total score

The endpoints relating to the 6th secondary objective are:

- Change from baseline at Weeks 52 and 104 in expressive language AEq score as assessed by the BSID-III language subtests or the KABC-II Expressive Vocabulary subtest, and the VABS-II communication domain

- Change from baseline at Weeks 52 and 104 in receptive language AEq score as assessed by the BSID-III language subtests or the KABC-II Expressive Vocabulary subtest, and the VABS-II communication domain

The endpoints relating to the 7th secondary objective are:

- Change from baseline at Weeks 52 and 104 in gross motor function AEq score as assessed by the BSID-III motor subtests and the VABS-II

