### **7.5.3.3 Magnetic resonance imaging**

Brain and abdominal MRI are performed under general anesthesia at Weeks 52 and 104.

MRI scanning protocols including details on sequence parameters and scanning guidelines are provided to the clinical sites under the coordination of the central MRI reader. MRI field strength should be a minimum of 1.5, preferable, 3.0 tesla.

Preferably, the same MRI technician should perform all study related scans. The separate MRI assessment protocol provided prior to the study start should be followed for each scan. MRI data are sent to the central reader for quantitative analyses.

The brain MRI assessment protocol includes:

1. 3D T1-weighted MPRAGE (~6 min) for volumetric analysis
2. DTI and gre fieldmap (~10 min) for white matter analysis
3. 3D FLAIR and T2 (~8 min) for volumetric analysis
4. 4.SWI (~10 min) for iron content analysis

The abdominal MRI assessment protocol includes:

1. T1 3D VIBE (~2 min.)
2. T2 HASTE (~2 min.)

Liver/spleen volumes are evaluated by MRI using a standard MRI protocol.

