11.1 Demographics

Individual patient demographics (age, gender and race) and body measurement data (height, weight, body mass index and head circumference) at study start will be listed.

Age will be counted in months. Height will be measured in centimetres and weight in kilograms. BMI (kg/m²) will be calculated from the height and weight.

These demographic characteristics and body measurements will be summarized for the total safety analysis set and the pivotal sub group.

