14.5 The MRI endpoints

As listed in Section 3.5.4, the MRI endpoints refers to changes in gray matter volume, compound ventricular volume, FA and MD in corpus callosum and cerebral white matter, SWI in cerebral white matter and basal ganglia.

To assess the PD effect of SOBI003 on MRI, linear models are used to model the change from baseline in MRI as dependent variable, for both logged MRI and untransformed MRI, and baseline level and age as continuous covariates, and accumulated dose (including the FIH study) as covariate and sex as factor. The analyses are conducted for each assessment time point: week 52 and 104.

In addition, linear analyses with MRI levels, both logged MRI levels and untransformed MRI levels, as dependent variable, and baseline level and age as continuous covariates, and accumulated dose as covariate and sex as factor will be performed across all assessments (including the FIH study), with assessment as a repeated factor.

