14.7 Other efficacy endpoints

Endpoints relating to the neurocognition, liver and spleen volume, QoL, language, motor function and sleep pattern are summarized using descriptive statistics.

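### Liver and spleen effect is summarised as raw volume change over about two years in growing children, so treatment effect and growth cannot be separated

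*SAP*

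**What the plan says.** The objective, in SAP 3.3, is "To assess the effect of SOBI003 on liver and spleen volume". SAP 3.5.4 gives the liver endpoint as "Change from baseline at Weeks 52 and 104 in liver volume as assessed by abdominal MRI". Protocol 6.3.1 has the same pair of endpoints, for example "Change from baseline at Weeks 52 and 104 in spleen volume as assessed by abdominal MRI". SAP 4.1 takes baseline from the FIH study, so the Week 104 change spans about two years.

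On measurement, Protocol 7.5.3.3 says only "Liver/spleen volumes are evaluated by MRI using a standard MRI protocol". On analysis, SAP 14.7 says "Endpoints relating to the neurocognition, liver and spleen volume, QoL, language, motor function and sleep pattern are summarized using descriptive statistics", and Protocol 9.4.4.2 agrees.

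The SAP also has regression models for imaging: "To assess the PD effect of SOBI003 on MRI, linear models are used to model the change from baseline in MRI as dependent variable" (SAP 14.5). That section defines its scope by saying that "the MRI endpoints refers to changes in gray matter volume, compound ventricular volume, FA and MD in corpus callosum and cerebral white matter", followed by susceptibility-weighted measures of white matter and basal ganglia. Liver and spleen are not in the list.

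SAP 4.3.1 defines the natural history control group for the DQ endpoint. No control is named for organ volume.

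Body size is measured. SAP 11.1 states that "body measurement data (height, weight, body mass index and head circumference) at study start will be listed", and Protocol Table 7 schedules height and weight on Day 7 of Weeks 52 and 104, with the MRI on Day 2. Neither document uses these measurements in the liver or spleen endpoints.

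**The concern.** The intended population is young. SAP 4.2 aims for patients as close as possible to the natural history study, whose comparison group was 12 to 72 months old at baseline. A child of that age grows over two years, and the liver and spleen are expected to grow with the child.

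The hoped-for drug effect runs the other way: Protocol 5.1.3 reports lower liver and spleen weights in treated MPS IIIA mice. Raw volume change is the net of these two movements. In a single arm with no control or growth reference for organ volume, nothing in the planned summary removes the growth part.

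At stake is how objective 4 is read. A mean change near zero could mean that the drug does nothing and growth was slight, or that the drug shrinks the organ relative to the child and growth made up the difference. The planned tables would not distinguish these cases.

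**Working it through.** **Figure to reproduce.** There is none. The documents give no sample size, effect size, standard deviation, baseline volume or growth rate for liver or spleen. The only power statements (Protocol 9.1, SAP 7.1) concern DQ and CSF heparan sulfate.

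**Set-up.** Let g be the proportional growth, from baseline to the scan, in the organ volume expected for the child's size. Let r be the true proportional reduction relative to that expected size. Both are assumptions. Then

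raw change = (1 + g)(1 - r) - 1.

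The reduction is fully masked (raw change of zero) when g = r/(1 - r).

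**Results over an assumed range:**

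| True relative reduction r | g = 10% | g = 20% | g = 30% | g = 40% | g = 50% | Growth that fully masks it |
|---|---|---|---|---|---|---|
| 10% | -1% | +8% | +17% | +26% | +35% | 11.1% |
| 20% | -12% | -4% | +4% | +12% | +20% | 25.0% |
| 30% | -23% | -16% | -9% | -2% | +5% | 42.9% |
| 40% | -34% | -28% | -22% | -16% | -10% | 66.7% |

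Example cell: r = 20%, g = 30% gives 1.30 × 0.80 - 1 = +4%. Example masking point: 0.20/0.80 = 25%.

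**Reading backwards from a result.** A raw change of +8% fits no effect with 8% growth. It equally fits a 10% reduction with 20% growth (1.20 × 0.90 = 1.08) or a 20% reduction with 35% growth (1.35 × 0.80 = 1.08). The raw figure alone cannot choose between them. A raw change of -4% fits a 20% reduction with 20% growth (1.20 × 0.80 = 0.96), so with any positive growth a fall is smaller than the true relative reduction.

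**Effect of scaling.** Let h be the proportional weight gain. Then

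change per kg = (1 + g)(1 - r)/(1 + h) - 1.

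If expected organ volume tracks weight (h = g), this returns -r in every cell. If weight lags, it does not: r = 20%, g = 30%, h = 20% gives 1.04/1.20 - 1 = -13.3%. That is short of -20%, but in the right direction, where the raw change shows +4%.

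**The case against.** **The imaging models adjust for age.** They do not reach these endpoints: SAP 14.5 lists brain measures only, and SAP 14.7 assigns liver and spleen to descriptive statistics. Even where such a model applies, baseline and age covariates account for differences between children. They do not subtract the average growth contained in a single arm's mean change.

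**The harm is not quantified by the documents.** This stands. They do not give weight gain, baseline organ volumes or an expected reduction in humans, or say that these patients' organs are enlarged. The direction of the problem is secure; its size is not.

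**Volume per kg is imperfect.** This also stands. It assumes that organ volume tracks weight, and Protocol 5.1.1 describes late-stage swallowing difficulties, sometimes requiring gastrostomy feeding. Poor weight gain would raise mL/kg with no change in the organ. That is a reason to report both measures, not to rely on raw volume alone.

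**Nothing is lost irreversibly.** True: weights are collected, SAP 9 lists all data by patient, and SAP 2 allows exploratory analyses beyond those it names. But a scaling chosen after the results are seen carries less weight than one fixed beforehand.

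**Stronger readings a reader might infer:**
- *Objective 4 cannot be answered.* Not supported: a reduction larger than growth still appears as a fall, as the 40% row shows.
- *The 4-weekly weighing shows that the protocol recognises growth as a problem for these endpoints.* Not supported: Protocol 7.5.4.6.1 gives dose calculation as its purpose.
- *Gray matter and ventricular volumes have the same defect.* Not established: they are modelled under SAP 14.5, and are determined centrally under a study-specific MRI manual (Protocol 4.4) that is not among the documents and may or may not address head size.

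**Conclusion.** The point holds as a limitation of the planned summary. Liver and spleen are assessed by unscaled change over about 104 weeks in a single arm of growing children, so treatment effect and growth cannot be told apart. A null or positive raw change is uninterpretable, and a fall understates the effect. Under the assumed growth of 10% to 50%, small and moderate reductions can vanish or change sign, while a large one is diluted but remains visible.

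The conclusion rests on two assumptions: that expected organ volume rises over the study, and that any drug effect is downward. The percentages are illustrations only.

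This concerns one of ten numbered secondary objectives, untested and outside the hierarchy, in a study whose primary objective is safety. The appropriate label is a cheap improvement.

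**What to change.** Before database lock, in SAP 3.5.4 and 14.7:

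- Add change from baseline at Weeks 52 and 104 in liver volume and in spleen volume per kg body weight (mL/kg).
- State the pairing of scan and weight: the FIH baseline scan with the FIH baseline weight, and the Week 52 and Week 104 scans with the Day 7 weight of the same week. The two on-study scans are on Day 2, so the gap is five days.
- Report the per-kg change alongside the raw change in the same descriptive table, so that a reader can see whether a difference comes from the organ or from the weight.

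The cost is SAP wording, one derived variable per organ and a few table rows. No visit, scan or sample is added. SAP 5.2 already pools each patient's FIH safety and efficacy data with this study, so the FIH baseline values should be to hand. The downside is the dependence of mL/kg on weight gain, which is why raw volume stays alongside it.
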